7. STATISTICAL CONSIDERATIONS

7.1 Data analysis

Data analysis and statistical evaluation will be the responsibility of the primary investigator ([name]) using statistician resources at UH Cleveland Medical Center Harrington Heart and Vascular Institute (CWRU CTSC Biostatistics Core). Data will be collected in a secure REDCap database that is housed at our institution in accordance with local IRB regulations. Blinding will be maintained by the study team. Medications given to subjects will be labeled "study medication" to maintain subject blinding to treatment status and will be dispensed by the UHCMC Research Pharmacy for each subject after successful enrollment. For the purpose of the final analysis, the official clinical database will not be unblinded until medical/scientific review has been completed, protocol violators have been identified (if appropriate), and data has been declared complete.

7.2 Statistical analysis

The results of experiments will be analyzed by several statistical methods. Continuous variables will be analysis as the group mean and standard deviation. Categorical variables will be analyzed with a χ^2 test between groups. Continuous variables will be analyzed with t test for normally distributed variables and Wilcoxon 2 sample test for skewed distribution continuous variables. ANOVA will be used for evaluation of multiple continuous variables between groups. Curve fitting functions will be used for the detection of associations, using standard software (e.g., Graph pad prism 5.0). In all cases, p<0.05 will be considered as statistical significance.

Sample Size and Power Calculations: Our power analysis is based on physiologic outcome measures of primary and secondary endpoints estimated from the reported literature on heart failure with preserved ejection fraction. Power calculations were performed in R software.

For the primary endpoint, peak exercise oxygen uptake (VO2 peak), increased VO2 peak is a marker for reduced mortality and morbidity with associated increase in cardiopulmonary fitness in heart failure with preserved ejection fraction patients.25, 26 The primary endpoint for this trial is increase in VO2 over the duration of the study period. Baseline peak VO2 exercise performance in HFpEF has been reliably reported at 11.7 ml/kg/min in the RELAX trial26 with a within-patient standard deviation for peak VO2 in HFpEF of 2.0 ml/kg/min (used for both INDIE-HFpEF and RELAX trials).25,26 To calculate the primary endpoint power, the ss.1way function with variables: (k=2, alpha=0.05, beta=.2, f=.4, B=100) was used. For a power of 80%, assuming 5% type I error and a standard deviation of 2.0 ml/kg/min, we must enroll 26 subjects to detect a 2.0 ml/kg/min change from baseline in peak VO2 difference between the mean of placebo and ertugliflozin groups based on power calculation.

A secondary endpoint of left ventricular mass by CMRI (measured concurrently to VO2 during Ex-CMR protocol) will be measured. Reduced left ventricular (LV) mass is a marker of response to heart failure therapy. A reduction of LV mass by 10 gm has been reported as a significant marker of clinical response.24 (The same group reported a standard deviation of 9.6 gm for a 10 gm mean change in LV

mass in heart failure patients.30 For a power of 80% assuming 5% type I error, we must enroll 20 subjects to detect a 10 gm change in LV mass assuming a standard deviation of 9.6 gm.

A secondary endpoint of change in fasting serum β -hydroxybutyrate (μ mol/L) will be measured. Ferrannini et al. report fasting BHB levels of 246 (standard deviation 288) prior to exposure to empagliflozin21 with an increase to 561 after 4-week exposure to drug. For a power of 80%, assuming 5% type I error, we must enroll 18 subjects to detect a 125% increase in fasting serum β hydroxybutyrate.

	Parameter	Reference	δ (Change)	SD (ơ)	N (90% power)
Primary Endpoint:					
Oxygen uptake	VO ₂ (ml/kg//min)	25, 26	2.0	2.0	21
Secondary Endpoints					
Ventricular Mass (measured by CMRI)	MRI measured LV Mass (gm)	24	5	4	14

21

125

117

18

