3. STUDY DESIGN

The EMMED-HF trial will be a single blinded (to patient), randomized, parallel group, active controlled, single center experimental design. 52 subjects with HFpEF and DM2 will comorbidities will be recruited to participate (N = 26 ertugliflozin group, N = 26 placebo group) with a 12 week study intervention period.

Enrollment/Randomization procedure

Subjects will be screened by qualified practitioners for eligibility to participate in the EMMED-HF clinical study. Once the subject has been determined to be eligible, an enrollment visit will be scheduled. Those subjects that meet the inclusion criteria and do not possess any exclusion criteria will be deemed eligible for enrollment by key study personnel and then undergo randomization to treatment arm. Randomization into treatment group will occur at baseline at a 1:1 ratio.

Primary endpoint

The primary endpoint is to assess the degree of change in peak exercise oxygen uptake (peak VO2, ml/kg/min) as measured by metabolic gas exchange during a MRIcardiopulmonary exercise test (CPET-ExMR) protocol.

Secondary endpoints

Change in LV mass index (gm/m2) measured by MRI imaging will be a pre-specified secondary endpoint. An additional pre-specified secondary endpoint will be fasting serum β -hydroxybutyrate (ketone body).

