Transthoracic Echocardiography: Standard echocardiography windows will be acquired with special focus on left ventricular ejection fraction (LV EF), LV size, LV wall mass, diastology (mitral inflow velocities, tissue Doppler velocities), left ventricular global longitudinal strain imaging via Speckle tracking (Q Lab 9.0 Philips package), left atrial size and right ventricular systolic pressure as measured by tricuspid regurgitant velocity. All 52 subjects will undergo echo imaging at baseline and study completion in the Mather Pavilion 1800 echo lab. Echocardiography protocols will be supervised by the primary investigator, [name].

Cardiopulmonary Exercise Cardiac Magnetic Resonance Imaging (CPET-ExMR): The CPET-ExMR exercise protocol, combining metabolic exercise testing assessing exercise oxygen consumption (VO2) performed on an MRI-compatible bicycle ergometer or hydraulic treadmill in combination with a MRI stress test (baseline and peak exercise imaging) will be performed at baseline. All subjects will complete the CPET-ExMR prior to starting study drug. CPET-ExMR testing provides whole body metabolic assessment including peak VO2 oxygen consumption, resting metabolic substrate (measured by resting respiratory exchange ratio [RER]), and ventilatory efficiency (VE/VCO2). Cardiac function will be assessed by MRI sequences to quantitate LV mass, LVEF, diastolic and systolic function, extracellular volume fraction (ECV), and tissue edema using T2 mapping.

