Visit #3: Follow up Testing: At the end of the study intervention period, but prior to the completion of the study medication package (during week #12), the subject will undergo a repeat of the same battery of clinical testing as during Visit #2. Each test will be conducted with an identical protocol to allow for intra-subject assessment of change. Testing during Visit #3 will include: Transthoracic Echocardiography

Cardiopulmonary Exercise Cardiac Magnetic Resonance Imaging (CPET-ExMR) Dual-energy absorptiometry (DEXA) Serum Chemistries & Metabolomics

Symptom Surveys

Study Completion: At the end of the 12 week intervention period, after the subject has completed screening (visit #1), baseline (visit #2), and end of study (visit #3) testing, a SUBJECT COMPLETION CRF must be completed. During the course of the study, it is possible that subjects will be withdrawn from the study. Factors leading to Subject early termination may include, but are not limited to the following.

Subject Withdrawal - A Subject may voluntarily withdraw from the study at any time without affecting their future medical treatment or benefits. In addition, the Investigator may withdraw a Subject from the study if the enrolled Subject does not meet the inclusion/exclusion criteria,

refuses further testing or follow-up evaluations, or for any other reason as determined by the Investigator. A SUBJECT TERMINATION CRF must be completed.

Subject Lost to Follow-Up – If the Investigator has attempted to contact a Subject at least three times and receives no response, the Subject is considered lost to follow-up. The research staff should document at minimum three attempts to contact the Subject, including a certified letter, prior to terminating a Subject from the trial. A SUBJECT COMPLETION CRF must be completed. Subject Death – The Investigator will notify the UH IRB, the local DSMB, the FDA and the Sponsor within 7 days of knowledge of a subject's death. An ADVERSE EVENT and SUBJECT COMPLETION CRF must be completed, as well as a report from the Investigator explaining the nature of the Subject's death.

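### Baseline peak VO2 enters the primary comparison only by subtraction; adjusting for it by ANCOVA would cut the variance by about 23% to 8% (assumed correlation 0.5 to 0.8), at almost no cost

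*Combined protocol and SAP*

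**What the plan says.** Section 7.2 sets the between-arm tests generically: "Continuous variables will be analyzed with t test for normally distributed variables and Wilcoxon 2 sample test for skewed distribution continuous variables". It adds that "ANOVA will be used for evaluation of multiple continuous variables between groups". The text we have contains no ANCOVA, covariate or baseline adjustment. The curve-fitting functions mentioned there are for finding associations, not for comparing the arms.

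No test is tied to peak VO2 by name, but the form of the variable is clear. Section 3 states: "The primary endpoint is to assess the degree of change in peak exercise oxygen uptake". The sample-size paragraph in section 7.2 targets a 2.0 ml/kg/min "change from baseline in peak VO2 difference between the mean of placebo and ertugliflozin groups".

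Baseline is collected in everyone. Section 4.4 says of the baseline visit, "All subjects will complete the CPET-ExMR prior to starting study drug", and of the week-12 visit, "Each test will be conducted with an identical protocol to allow for intra-subject assessment of change".

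**The concern.** A t test on change fixes the coefficient of baseline at 1. ANCOVA estimates that coefficient from the data. Unless week-12 peak VO2 tracks baseline almost one for one, subtracting the whole baseline value carries baseline noise into the outcome, and the treatment effect is estimated less precisely than it could be from the same 52 subjects.

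This is a matter of efficiency, not bias. It matters because the trial is small and the planned power is only just above 80% with all 52 subjects evaluable. The text we have states no allowance for dropout, although section 4.4 provides for withdrawal and loss to follow-up. Adjustment also has to be pre-specified: added after unblinding, it would look data-driven.

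**Working it through.** **Inputs from the documents.** 26 per arm (N = 52), 1:1 allocation (section 3). Two-sided alpha 0.05, power 80%, f = 0.4, SD 2.0 ml/kg/min, difference 2.0 ml/kg/min (section 7.2).

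**Assumed inputs.** Baseline to week-12 correlation ρ of 0.5 to 0.8, with 0.9 and 0.95 as extremes. Equal variances at the two visits (relaxed in step 5). The 2.0 is read as the SD of the change, because the section 7.2 table pairs it with a change of 2.0.

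**1. The plan's own figure.** With two groups, f = 0.4 is a standardised difference d = 2f = 0.8. By the exact noncentral t, 26 per arm gives 80.7% power and is the smallest size that reaches 80%. The stated 26 is reproduced, read as per arm.

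**2. Variance ratio.** With common visit variance σ²:

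- change score: variance per subject 2σ²(1 − ρ)
- ANCOVA: variance per subject σ²(1 − ρ²)
- ratio: (1 − ρ²) / [2(1 − ρ)] = (1 + ρ)/2

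Estimating the slope multiplies this by 1 + 1/(N − 4) = 49/48. At ρ = 0.5 the ratio is 0.75 × 49/48 = 0.766, a 23.4% reduction. Break-even is where (1 + ρ)/2 × 49/48 = 1, that is ρ = 2 × 48/49 − 1 = 0.96.

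**3. Confidence interval.** The 95% half-width for the change score is t(0.975, 50) × 2.0 × √(2/26) = 1.11 ml/kg/min. For ANCOVA it is t(0.975, 49) × 2.0 × √(ratio × 2/26).

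**4. Power.** Noncentral t with 50 df for the change score and 49 df for ANCOVA, where d becomes d/√ratio. With SD 2.0, d = 0.8 is a difference of 1.6 ml/kg/min, while the stated difference of 2.0 is d = 1.0. The plan's f and its stated difference do not agree. That is a separate matter, so both are shown.

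| Analysis | Variance reduction | 95% half-width | Power, d = 0.8 | Power, d = 1.0 | Change-score n per arm to match |
|---|---|---|---|---|---|
| Change score | – | 1.11 | 80.7% | 94.2% | 26 |
| ANCOVA, ρ 0.5 | 23.4% | 0.98 | 89.8% | 98.1% | 34 |
| ANCOVA, ρ 0.7 | 13.2% | 1.04 | 85.9% | 96.7% | 30 |
| ANCOVA, ρ 0.8 | 8.1% | 1.07 | 83.9% | 95.8% | 29 |
| ANCOVA, ρ 0.9 | 3.0% | 1.10 | 81.9% | 94.8% | 27 |

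At ρ = 0.95 the variance reduction is 0.5%. Simulation of 100,000 trials gave reductions of 23.9%, 8.3% and 2.9% at ρ = 0.5, 0.8 and 0.9. In 20,000 simulated trials per setting, type I error was 0.046–0.051 for the change score and 0.048–0.051 for ANCOVA.

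**5. Unequal visit variances.** With k = SD(week 12)/SD(baseline), the ratio is k²(1 − ρ²)/(1 + k² − 2ρk) × 49/48.

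| k | ρ 0.5 | ρ 0.7 | ρ 0.8 |
|---|---|---|---|
| 0.9 | 31.9% lower | 23.3% lower | 19.5% lower |
| 1.1 | 16.5% lower | 6.0% lower | 1.2% lower |

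At k = 1.1 and ρ = 0.9 there is a loss of 2.0%. The loss can never exceed the slope factor: 49/48 − 1 = 2.1%.

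**The case against.** The best defence is that a randomised comparison of change scores is a legitimate primary analysis, and nothing here shows bias or an inflated type I error. That stands, and it limits the point to precision.

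The size of the gain also rests on a correlation that the documents do not give. With the SD of change held at 2.0 and equal visit variances, the visit SD is 2.0/√[2(1 − ρ)]: 2.0 at ρ = 0.5, 3.2 at 0.8 and 4.5 at 0.9. A varied population, and entry is allowed across ages 18 to 75 and BMI 25 to 42, would push ρ up and the gain down. This stands too: the gain may be small, and in some settings it is a loss of up to about 2%. At the stated difference of 2.0 with SD 2.0, power is already 94.2%, so little is added.

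The absolute figures depend on how the 2.0 is read. Section 7.2 calls it a "within-patient standard deviation for peak VO2 in HFpEF of 2.0 ml/kg/min". If that is a per-visit SD, with independent errors at the two visits, the SD of change is 2.0 × √2 = 2.83. The change-score half-width becomes 1.58, and power for a difference of 2.0 is 70.6%. The percentage reductions do not change, and under that reading the extra precision is worth more.

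Finally, the use of a change score is inferred from the endpoint definition. Aim 1 in section 1 names the endpoint simply as peak oxygen uptake. If week-12 values alone were compared, baseline would not be used at all, and ANCOVA would gain more at high correlation: about 63% of the variance at ρ = 0.8 in simulation.

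**Conclusion.** The point holds, as a recommended improvement and not as a fault that invalidates the trial. The plan names no baseline-adjusted analysis, although baseline peak VO2 is to be measured in every subject before study drug. With equal visit variances, adjustment lowers the variance of the primary effect by 23% to 8% for an assumed ρ of 0.5 to 0.8. This is equivalent to 8 to 3 more subjects per arm under the change-score test (34 − 26 to 29 − 26). At ρ = 0.9 the gain is 3%, and above about 0.96 there is none. The possible loss is capped at about 2%. That no covariate is specified is certain. The size of the benefit is not, because it depends on a correlation and a variance ratio that the documents do not report. No gain has been calculated for LV mass index or β-hydroxybutyrate, or against the Wilcoxon route.

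**What to change.** In section 7.2, name the primary analysis: a linear model (ANCOVA) of week-12 peak VO2 on arm and baseline peak VO2, reporting the adjusted difference between arms with its 95% confidence interval. Keep the Wilcoxon test on change as a sensitivity analysis, so that the choice of primary test does not depend on the observed distribution. The same model can be used for LV mass index, and for log β-hydroxybutyrate on its log baseline value.

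The cost is a few sentences in the plan and one degree of freedom. No new measurement, visit or subject is needed. The change should be made before the database is unblinded.

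### Section 7.2 does not say whether its SD of 2.0 ml/kg/min is for one peak VO2 reading or for the change; at its label, power at 26 per arm is about 71%

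*Combined protocol and SAP*

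**What the plan says.** Section 3 sets a parallel-group design, "N = 26 ertugliflozin group, N = 26 placebo group", with 1:1 randomization. The primary endpoint is the change in peak VO2 over 12 weeks.

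The sample-size paragraph of section 7.2 gives one variability figure for this endpoint, a "within-patient standard deviation for peak VO2 in HFpEF of 2.0 ml/kg/min (used for both INDIE-HFpEF and RELAX trials". It then sizes the trial "assuming 5% type I error and a standard deviation of 2.0 ml/kg/min", with the aim to "detect a 2.0 ml/kg/min change from baseline in peak VO2 difference between the mean of placebo and ertugliflozin groups". The software call it reports is ss.1way with "k=2, alpha=0.05, beta=.2, f=.4, B=100", and the result is 26.

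The table that closes section 7.2 gives a second sizing for the same endpoint: change 2.0, SD 2.0, N = 21 under a 90% power heading.

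For the analysis, 7.2 names a t test, or a Wilcoxon test for skewed data. It names no baseline-adjusted model and gives no correlation between baseline and follow-up.

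**The concern.** A two-arm comparison of change needs the between-subject SD of the change. A within-patient SD of peak VO2, in the ordinary sense, is the scatter of one patient's readings about that patient's own mean. A change score is the difference of two such readings and carries the error of both, so its SD is larger by a factor of √2 before any real differences in response are added. Section 7.2 makes no such conversion and does not say that the 2.0 is already an SD of change.

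This is the only variability input for the primary endpoint. If it is a per-visit SD, the stated power is too high, and a reader who relies on the 80% or 90% would place too much weight on a non-significant result.

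**Working it through.** **Inputs.** From section 7.2: α = 0.05, difference δ = 2.0 ml/kg/min, stated SD 2.0, f = 0.4, k = 2, power 80% in the text and 90% in the table. From section 3: 26 per arm, 1:1. Sidedness is not stated; I assume two-sided, which is what a one-way ANOVA with two groups amounts to. All 26 per arm are taken as analysed.

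**Method.** Power of the two-sample t test from the noncentral t, with 2n − 2 degrees of freedom and noncentrality (δ/SD) × √(n/2).

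**1. Reproduce the plan's 26.** With two groups d = 2f = 0.8. Power is 79.2% at 25 per arm and 80.7% at 26, so 26 per arm reproduces. At δ = 2.0, d = 0.8 implies SD = 2.0/0.8 = 2.5. The worded inputs (2.0 and 2.0, d = 1.0) would need only 17 per arm for 80%, so the SD of 2.0 did not produce the 26.

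**2. Reproduce the table's 21.** Normal approximation: n = 2 × (1.960 + 1.282)² × (2.0/2.0)² = 21.01 per arm. This sizing does use 2.0 and 2.0. Rounded up it is 22, and the t test needs 23.

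**3. What SD can 26 per arm tolerate?** For 80% power at 26 per arm, d must be at least 0.792. At δ = 2.0 the SD of change can be at most 2.0/0.792 = 2.52.

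**4. SD of change if 2.0 is a per-visit within-patient SD.** With errors independent between visits and no variation in true response, Var(change) = 2.0² + 2.0² = 8, so SD = 2.83. Variation in true response would raise it.

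**5. Power for δ = 2.0 under each SD.**

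| SD of change | Where it comes from | 26 per arm | 21 per arm |
|---|---|---|---|
| 2.0 | the 2.0 is already the SD of change | 94.2% | 88.5% |
| 2.5 | implied by f = 0.4 | 80.7% | 71.6% |
| 2.83 | the 2.0 is a per-visit SD | 70.6% | 60.9% |

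At SD 2.83, 80% power needs 33 per arm (32 gives 79.5%). The difference detectable with 80% power at 26 per arm is 0.792 × 2.83 = 2.24.

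**6. Effect of adjusting for baseline.** With equal variance σ² at both visits and correlation r, the within-patient variance is σ²(1 − r) = 2.0². With baseline as covariate the residual variance is σ²(1 − r²) = 2.0²(1 + r), so the residual SD is 2.0 × √(1 + r). The documents give no r; 0.5 to 0.8 is assumed.

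- r = 0.5: SD 2.45, power 82%
- r = 0.6: SD 2.53, power 80%
- r = 0.7: SD 2.61, power 77%
- r = 0.8: SD 2.68, power 75%

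**The case against.** The strongest objection is that the √2 step rests on one reading of a loose phrase. The 2.0 may be the SD of within-patient change. Some context favours that: the table sets its SD column beside a column of changes, the LV mass text describes its SD as belonging to a mean change, and the 2.0 is paired directly with a change from baseline. Against this, the β-hydroxybutyrate text takes its SD from a pre-treatment level. The two cited HFpEF trials would settle the matter but are not part of the documents. This objection stands, and it makes the conclusion conditional.

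A second objection also stands. A reader might infer that the 26 per arm was computed with an SD of 2.0, so that the variability is understated by the full step from 2.0 to 2.83. Step 1 shows otherwise: f = 0.4 already carries an SD of 2.5. The gap that matters is 2.83 against a tolerable 2.52.

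Third, it is tempting to say that a null result would falsely rule out a 2.0 ml/kg/min effect. That depends on the confidence interval. At SD 2.83 and 26 per arm the 95% half-width is 2.009 × 2.83 × √(2/26) = 1.58. An observed difference below 2.0 − 1.58 = 0.42 would validly exclude 2.0; non-significant estimates from about 0.42 to 1.58 would not.

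What survives is that 7.2 needs correcting under either reading. If the label is right, the stated power is wrong. If the 2.0 is an SD of change, the label is wrong.

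**Conclusion.** The point holds in conditional form. Section 7.2 applies a figure labelled a within-patient SD to a between-arm comparison of change, without converting it. Taken at its label, the SD of change is at least 2.83: power for 2.0 ml/kg/min is at most about 71% at 26 per arm and 61% at 21, where the plan states 80% and 90%. If the 2.0 is already the SD of change, power at 26 per arm is about 94%.

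A reader might infer that the trial is shown to be underpowered. The documents do not support that; they support a range of about 71% to 94% that hangs on one undefined input. The 71% assumes a two-sided 0.05 test, independent errors between visits, equal response in all patients, no baseline adjustment and no dropout. Unequal response or dropout would lower it; baseline adjustment would raise it.

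**What to change.** In section 7.2:

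1. Say what the 2.0 is, and give the SD of the 12-week change in peak VO2.
2. Restate power or the detectable difference at 26 per arm on that SD. If the 2.0 is per visit, this is about 71%, or 2.24 ml/kg/min at 80% power, for the unadjusted test. With baseline peak VO2 as a covariate it is 75% to 82% for an assumed r of 0.8 to 0.5; in that case name the model and state r.
3. If the 2.0 is the SD of change, correct the label and state about 94%.
4. Make f and the table row (21 at 90%) follow from the same SD.

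The cost is a few lines of text and one table row. The sample size need not change. The downside, if the label is right, is a less favourable stated power.

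### The stated basis for 26 per group does not match its own R call: f = .4 means 1.6 ml/kg/min at SD 2.0 (or 2.0 at SD 2.5), not 2.0 at SD 2.0

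*Combined protocol and SAP*

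**What the plan says.** Sections 1 (Aim 1) and 3 plan 52 subjects, 26 per arm, randomised 1:1. The justification is in section 7.2, under Sample Size and Power Calculations.

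- **Software call.** The `ss.1way` function in R was run with "k=2, alpha=0.05, beta=.2, f=.4, B=100".
- **Result as stated.** The conclusion drawn for the comparison of ertugliflozin with placebo is that "we must enroll 26 subjects to detect a 2.0 ml/kg/min change from baseline in peak VO2 difference". It is stated at 80% power with an SD of 2.0.
- **Source of the SD.** It is described as a "within-patient standard deviation for peak VO2 in HFpEF of 2.0 ml/kg/min", taken from two earlier HFpEF trials. The endpoint it is applied to is a change: "The primary endpoint for this trial is increase in VO2 over the duration of the study period".
- **Power table.** The peak VO2 row has change 2.0, SD 2.0 and N = 21, under a column headed 90% power.
- **LV mass.** The text says "For a power of 80% assuming 5% type I error, we must enroll 20 subjects to detect a 10 gm change in LV mass", with SD 9.6 gm. The table row has a change of 5, SD 4 and N = 14 at 90% power, also in grams. Sections 1 and 3 define the endpoint in gm/m2.
- **Fasting beta-hydroxybutyrate.** The text says "For a power of 80%, assuming 5% type I error, we must enroll 18 subjects to detect a 125% increase in fasting serum" beta-hydroxybutyrate, citing a mean of 246 (SD 288) rising to 561.

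**The concern.** The R call and the sentence that follows it give the same 26 but imply different effect sizes. The table then gives a smaller N at a higher power for the sentence's own difference and SD, and that is impossible within one calculation. A reader cannot tell whether the trial was sized for a difference of 1.6 or 2.0 ml/kg/min, or with an SD of change of 2.0 or 2.5.

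This matters when the result is read. If peak VO2 shows no significant difference, the report will need to say which difference the trial was built to detect. A statement of 80% power for 2.0 at SD 2.0, carried forward from the protocol, would be wrong. The secondary-endpoint figures raise the same traceability problem.

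**Working it through.** **Method.** Two equal groups, two-sided alpha 0.05, N per group. For two groups f = d/2, where d = difference/SD. Exact power is from the noncentral F with 1 and 2n − 2 df (equivalent to the two-sided t test). The normal approximation is n = 2(z₀.₉₇₅ + z_power)²/d².

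**1. The plan's 26.** f = .4 gives d = 0.8. Exact power is 79.1% at n = 25 and 80.7% at n = 26. So the call as printed reproduces 26 per group, matching sections 1 and 3.

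**2. What d = 0.8 means.** At SD 2.0 the difference is 0.8 × 2.0 = 1.6 ml/kg/min. For a difference of 2.0 the SD is 2.0/0.8 = 2.5. Section 7.2 gives neither 1.6 nor 2.5.

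**3. The sentence's own inputs.** 2.0/2.0 gives d = 1.0, f = .5. Exact 80% power needs 17 per group (80.7%; 78.1% at 16). At 26 per group power is 94.2%.

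**4. The table's 21.** For d = 1.0 at 90% power the normal approximation gives 2(1.960 + 1.282)² = 21.01, with power 89.98% at 21. The table evidently uses this formula, rounded to 21; strict rounding up gives 22 and the t test 23. Either way, 90% power cannot need fewer subjects than 80% power for the same inputs.

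**5. Secondary endpoints**, read as N per group like the primary (the text does not label them):

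| Endpoint and inputs | d | N at 80%, normal / t | N at 90%, normal | Plan | Power at 26 (t) |
|---|---|---|---|---|---|
| LV mass 10/9.6 (text) | 1.042 | 14.47 → 15 / 16 | 19.37 → 20 | 20, labelled 80% | 95.8% |
| LV mass 5/4 (table) | 1.25 | – | 13.45 → 14 | 14, labelled 90% | 99.3% |
| Beta-hydroxybutyrate (561 − 246)/288 = 315/288 (text) | 1.094 | 13.12 → 14 / 15 | 17.57 → 18 | 18, labelled 80% | 97.2% |

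The text's 20 and 18 are what the normal approximation gives at 90%, so the 80% label looks like a slip. The table's beta-hydroxybutyrate row is broken in the available copy and is not used here.

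**6. Meaning of the SD.** With 26 per group, power for a difference of 2.0 stays at or above 80% while the SD of change is at most 2.0/0.7923 = 2.52. The documents do not say that 2.0 is the SD of the 12-week change. The correlations and error model below are assumptions, not document figures.

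| Assumed meaning of 2.0 | SD of change | Power for 2.0 at 26 per group |
|---|---|---|
| SD of change | 2.00 | 94.2% |
| Cross-sectional SD, pre/post correlation 0.3: 2.0√(2 × 0.7) | 2.37 | 85% |
| Same, correlation 0.5 | 2.00 | 94% |
| Same, correlation 0.7 | 1.55 | 99.5% |
| Single-measurement error SD, independent errors, no variation in response: 2.0√2 | 2.83 | about 71% |

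In the last case, variation in response would lower the power further.

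**The case against.** **The error is conservative.** Taken literally, 2.0 at SD 2.0 gives 94.2% power with 26 per group, and 26 exceeds every secondary N quoted. No visit, analysis or decision rule depends on the sentence. This stands, and it is why the point concerns stated figures and not trial size.

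**The 26 could come from another route.** A dropout allowance on a 90% figure could reach 26: 23/(1 − 0.10) = 25.6, or 21 × 1.2 = 25.2. But no allowance is stated, the text ties 26 to 80% power, and the printed call returns exactly 26. Reading 26 as a total fails because sections 1 and 3 put 26 in each arm. A one-sided reading conflicts with the two-group ANOVA call.

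**The label slip is inferred.** This is fair. By the t test 20 and 18 fall just short of 90% (89.4% and 89.0%). The stated 125% rise is 1.25 × 246 = 307.5, not 315; 307.5/288 needs 18.43 at 90% by the normal approximation. Even so, both figures sit near 90%, and neither is the minimum N for 80%.

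**The authors probably mean 2.0 as the SD of change.** That is the natural reading of the sentence and the table. It still needs saying, because the term used can mean something else. The 71% case is only the pessimistic end of an assumed range.

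**Conclusion.** The concern holds. The reported call supports 26 per group at 80.7% power for a standardised difference of 0.8. The sentence claims that N for a standardised difference of 1.0, which needs 17 per group and has 94.2% power at 26. The table's 21 at 90% cannot stand beside 26 at 80% for the same inputs. The documents do not show which of f, the difference or the SD was intended. These results assume a two-sided 5% test, equal groups and 26 analysed per arm.

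The two LV mass input pairs and the mismatch between gm and gm/m2 are also plain contradictions. The mislabelled secondary powers are a strong inference. The meaning of the 2.0 SD is a point to clarify.

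The trial is not shown to be underpowered. The basis given for its size is wrong as written and should be corrected.

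**What to change.** Restate the calculation once in section 7.2:

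- **Primary endpoint.** Give N per group with one difference, one SD of change, one power and the test used. For example: 26 per group gives about 80% power for a between-group difference in change of 1.6 ml/kg/min, and about 94% for 2.0, if the SD of change is 2.0. If the call was meant for a difference of 2.0, state that it implies an SD of change of 2.5 and give its source.
- **SD.** Say whether the 2.0 is the SD of the 12-week change. If it is not, recompute power from that SD and show a range; above 2.52, power for 2.0 at 26 per group falls below 80%.
- **Table.** Make the peak VO2 row agree with the text on N and power.
- **Secondary endpoints.** Either relabel 20 and 18 as about 90% power or give the 80% figures (15 and 14 by the normal approximation, 16 and 15 by the t test). Name the formula and the beta-hydroxybutyrate difference used.
- **LV mass.** Use one difference and SD pair, in gm/m2.

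The cost is protocol wording and one table. The correction itself calls for no change to N, visits or data collection.
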